This study will test the feasibility of a smartband/smartphone-based smoking detection and brief mindfulness intervention (Fig 1), described in detail below. An initial pilot study will be run using the same approach (N=10). First, smokers will wear a smartband for 21 days to automatically monitor and detect smoking and will be notified of smoking episodes in real time to bring attention to their smoking behavior. Their smoking data from this time will be used to develop individualized smoking profiles. They will be instructed to smoke as much or as little as they like [68] but will set a quit date at 30 days. This timing was chosen to balance motivation to quit with time to collect enough smoking tracking data to predict smoking behavior. All subjects will be encouraged at study onset to utilize quit smoking medications to help cope with nicotine withdrawal, to meet clinical guidelines [71] and as in our prior work [72] by directing them to the medications and nicotine replacement therapy pages of <http://smokefree.gov>. Next, they will be provided with information on how mindfulness could be useful to smokers and will be introduced to the brief mindfulness exercises as part of an online mindfulness training (15 min). The “mindful smoking” exercise will then be triggered by any detected smoking episode for 7 days prior to their quit date, to bring awareness to the present moment effects of smoking. Finally, for 30 days post-quit, the RAIN exercise will be delivered to smokers prior to each predicted smoking episode according to their individualized smoking profile, to help them cope with cravings. They will continue to wear the smartband to monitor for smoking, and any detected smoking episode (i.e., relapse) will trigger the mindful smoking exercise. More generally, smokers can “delay” or “skip” any mindfulness exercise and will be compensated for wearing the smartband as described below. Additionally, the mindfulness exercises will be accessible in their previous text messages for the smoker to use any time they have a craving to smoke. All interactions with the smartband app will be time stamped including onset/offset of mindfulness exercises. This trial will test the feasibility of the intervention including treatment fidelity, adherence and acceptability, to inform a larger randomized controlled efficacy trial.

[figure not shown]

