For the subsequent 30 days, the RAIN exercise will be automatically delivered to the user via the smartphone app prior to each predicted smoking episode according to individual smoking profiles obtained as described below. They will first be asked to rate their craving (“How much are you craving a cigarette?” VAS “very much” to “not at all”) and affect (“How are you feeling?” VAS “very bad” to “very good” ¹⁰⁵). Next, they will be prompted to complete the RAIN exercise, also delivered as a 2-minute audio-guided mindfulness practice with subtitles. After completing RAIN, they will be asked “How helpful did you find this exercise?” (VAS “very helpful” to “not at all”); “How was the timing of this exercise?” (VAS “too early” to “too late”); and to again rate their craving and affect.

D.9. Individualized smoking profiles

Individualized smoking profiles will be obtained using smartband data tracking smoking across the first 21 days of the study, based on the maximum information possible: (1) average times each cigarette is smoked each day; (2) average times each cigarette is smoked on weekdays versus weekends; (3) average time between cigarettes; (4) average wake/sleep time; and (5) average cigarettes per day each day. Less predictable smokers will have less data to inform the prediction algorithm. At the very least, their waking hours will be divided by the number of cigarettes smoked per day and a prompt will be sent at random times in each interval. How much smartband tracking data is needed to adequately develop an individualized smoking profile is a main question in this feasibility trial. We will use this data to then deliver RAIN to the user for 30 days after their quit date. RAIN will be delivered 5 minutes prior to each predicted smoking episode during waking hours.

D.10. Adherence

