intervention: (1) Whether we can accurately detect smoking episodes will be determined by the percent of smoking episodes detected and the rate of false alarms in the first 21 days of the study during which smokers are wearing the smartband to track smoking and upon smoking detection are asked to confirm or deny smoking and self-report any undetected smoking episodes. We expect to replicate previous findings of >80% detection and negligible rate of false alarms [14]. (2) Whether we can deliver mindful smoking triggered by smoking episodes will be determined by the percent of mindful smoking exercises correctly triggered by detected smoking episodes and the rate of false alarms in the next 7 days of the study during which any detected smoking episode triggers a prompt that first asks the smoker to confirm or deny smoking and then launches the mindful smoking exercise. Again, we expect to replicate previous findings of >80% detection and negligible rate of false alarms [14]. (3) Whether we can deliver RAIN to predicted smoking episodes will be measured as average timeliness ratings in the next 30 days of the study during which RAIN is delivered prior to predicted smoking episodes and the smoker is asked to rate whether the exercise was delivered on time. Additionally, we will analyze the craving ratings obtained before participants complete RAIN, as a proxy for whether or not we have targeted moments of high craving. Ratings (Likert items for timeliness, craving) will be evaluated as % of participants and score range (very low, low, moderate, high, very high), with feasibility determined by 75% of participants rating an item (timeliness, craving) as moderate or higher. We expect on average moderate to high timeliness and craving ratings, suggesting that RAIN was delivered in time to help cope with cravings. These and other aspects of treatment fidelity will be reported according to recommended guidelines [17].

Aim 2. To assess adherence to a smartband/smartphone-based brief mindfulness intervention:

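### The plan calls the amount of tracking data needed for a smoking profile a main question, but Section 13 plans no analysis by amount of data

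*Combined protocol and SAP*

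**What the plan says.** Section D.9 (Individualized smoking profiles) sets the question: "How much smartband tracking data is needed to adequately develop an individualized smoking profile is a main question in this feasibility trial". The same section fixes the window: "Individualized smoking profiles will be obtained using smartband data tracking smoking across the first 21 days of the study". Section D.1 explains the schedule as a compromise and names no alternative length: "This timing was chosen to balance motivation to quit with time to collect enough smoking tracking data to predict smoking behavior". The ten-person pilot follows the same approach as the main trial.

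D.9 accepts that people will differ: "Less predictable smokers will have less data to inform the prediction algorithm". For them it gives a fallback, with the timing left to chance inside each interval: "At the very least, their waking hours will be divided by the number of cigarettes smoked per day and a prompt will be sent at" (the sentence is cut here). It sets no threshold for when the fallback applies.

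In Section 13, Aim 1(1) analyses the tracking period for the "percent of smoking episodes detected and the rate of false alarms in the first 21 days of the study". Aim 1(3) covers prediction: "Whether we can deliver RAIN to predicted smoking episodes will be measured as average timeliness ratings". Pre-RAIN craving is added as a proxy, and both ratings are judged by whether 75% of participants score moderate or higher. Under Aim 3, the User Experiences Questionnaire also has an item on whether exercises were timely.

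**The concern.** A question that the protocol itself calls a main one should have a measure, a contrast and a rule for reading the answer. Here there is one nominal window, no definition of an adequate profile, and no planned comparison of predicted with observed smoking times.

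The length of the tracking run-in is a design choice for the larger efficacy trial that this study is meant to inform. Under the plan as written, the team could report how well prompts from 21-day profiles were received. It would have no pre-specified basis for saying whether a shorter period would have served as well.

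**Working it through.** The documents give no figure for this question, so there is none to reproduce. The check has two parts: whether any planned analysis uses the amount of data, and whether the planned data could support one.

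**Planned analyses in Section 13, side by side**

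- Aim 1(1), first 21 days: detection and false alarms. This concerns the sensor, not the profile.
- Aim 1(2), next 7 days: correct triggering of mindful smoking. Triggering follows detected smoking, so no profile is involved.
- Aim 1(3), 30 days after quitting: timeliness and pre-RAIN craving. These bear on the profile but are not related to days, wear time or episodes tracked.
- Aim 2: wear time appears only as an adherence measure with an 80% cut-off.
- Aim 3: helpfulness and the questionnaire, including the timeliness item. Again there is no link to amount of data.
- Secondary analysis: cigarettes per day and abstinence. App interactions are to be related to engagement and secondary outcomes.

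None uses the amount of tracking data as a factor, a covariate or a truncation point.

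**Could the planned data support such an analysis?**

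Inputs: at least 5 cigarettes a day (inclusion criteria); 12 a day (mean of the earlier study cited under Aim 2); detection of 80% (Aim 1 expects more than this); wear of 80% (the Aim 2 cut-off).

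Nominal episodes per person = cigarettes per day × days.

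| Days | 5 per day | 12 per day | Weekend days |
|---|---|---|---|
| 7 | 35 | 84 | 2 |
| 14 | 70 | 168 | 4 |
| 21 | 105 | 252 | 6 |

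These are not floors. Participants may smoke as much or as little as they like, and the protocol cites evidence that tracking alone reduces smoking. Allowing for detection, the 21-day count at 5 a day is 105 × 0.80 = 84. With wear as well it is 84 × 0.80 = 67.2, about 67. At 12 a day the figures are 252 × 0.80 = 201.6 and 201.6 × 0.80 = 161.3. Self-reported misses would restore some of the loss.

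Assuming independent days of equal variance, the standard error of an average smoking time relative to the 21-day value is √(21/d). That is √(21/7) = 1.73 for 7 days, √(21/14) = 1.22 for 14, and 1.00 for 21. The expected gain from 14 to 21 days is therefore smaller than from 7 to 14. Whether it matters for placing a prompt is an empirical question.

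A held-out pre-quit week adds nominally 5 × 7 = 35 to 12 × 7 = 84 test episodes per person. A within-person comparison is therefore possible from data the trial already collects.

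**The case against.** The strongest reply is that the question appears in one sentence of D.9 and in none of the three aims, and that the stated goals are delivery, adherence and acceptability. This stands, and it limits the weight of the point: no aim and no feasibility decision changes.

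A second reply is that the amount of data will vary between people, through cigarettes per day, wear, detection and regularity, so it is not constant. That is true of the data. But no analysis uses the variation, and D.9 itself ties less data to less predictability. A comparison between people would mix amount with predictability and adherence. It would also be imprecise: for a correlation near zero, the approximate 95% half-width is 1.96/√(100 − 3) = 0.20 with 100 participants. With an assumed 53 (the 53% completion in the earlier app trial, applied to 100) it is 1.96/√(53 − 3) = 0.28.

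A reader might also infer more than the documents support:

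- That average timeliness is the only check on prediction. Pre-RAIN craving and the questionnaire item also bear on it.
- That 21-day profiles go untested. The ratings and their 75% criterion are a test, if an imperfect one. What goes untested is whether fewer days would do.
- That smoking times vanish after the quit date. The band stays on and lapses are still detected. They are a poor and selective reference for predicted habitual smoking, but they are not absent.
- That the trial could never answer the question. The gap is in the analysis plan, not in the data.

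**Conclusion.** The point holds in a limited form. D.9 declares a main question, and Section 13 contains no analysis that would answer it: there is one nominal window of 21 days and no planned contrast by amount of data. The existing timing measures could show that prompts from 21-day profiles were acceptable, but not how much tracking they required.

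This is a cheap improvement, not a flaw in the three formal aims. The judgement that the data are sufficient assumes that time-stamped confirmed and self-reported episodes can be extracted by day for each person. The episode counts are nominal, and the figure of 12 a day comes from an earlier study, not from this trial's population.

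**What to change.** Add to Section 13 a pre-specified, descriptive, within-person analysis:

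- Rebuild the profile averages listed in D.9 from each person's first 7, 14 and 21 tracking days, using time-stamped confirmed and self-reported episodes.
- Score the 7- and 14-day profiles on days 15–21. Score all three on the pre-quit mindful-smoking week, noting that the exercise may change smoking then.
- Define that week by calendar day. The stages add to 21 + 7 + 30 = 58 days, while the study is described as 60 days with a quit date at 30, so these passages need to be reconciled.
- Fix in advance the match window around a predicted time and the accuracy that counts as adequate.
- Report the share of cigarettes that fall near a predicted time and the predicted prompts with no cigarette. Show people on the random-prompt fallback separately.
- State the limits. The analysis can show whether fewer than 21 days suffice. If accuracy is still rising at 21 days, it can say only that 21 may be too few. Windows taken from the start are also the oldest, so any drift in smoking under tracking will count against the shorter ones.

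The alternative is to remove the statement that this is a main question.

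The cost is analysis time, with no new data collection. Section A.2 places profile generation on the vendor's platform, so vendor cooperation may be needed if the proprietary algorithm, and not just the listed averages, is to be re-run.

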- c. Include an appropriate Data and Safety Monitoring Plan. Examples of DSMPs are available here <http://your.yale.edu/policies-procedures/forms/420-fr-01-data-and-safety-monitoring-plans-templates> for
 - i. Minimal risk
 - ii. Greater than minimal

A formal Data and Safety Monitoring Plan has been made for this study in line with NCCIH guidelines (see attached).

Briefly, the Principal Investigator ([name]) will be responsible for assuring protocol compliance and conducting quarterly safety reviews which will be provided for review to the Independent Study Monitoring Committee. During the review process, the Principal Investigator will evaluate whether the study should continue unchanged, require modification/amendment, or close to enrollment.

This monitoring will be consistent with NIH policy regarding the protection of human subjects in research, and FDA guidance on statistical practices for clinical trials (ICH E9) and good clinical practices (ICH E6). In general, the data to be reviewed will include screening data, baseline data, efficacy data, and safety data.

This project presents minimal risks to the subjects and adverse events or other problems are not anticipated. The Principal Investigator will conduct a review of all adverse events and determine the attribution and grade of severity of the adverse event by using the following scales:

Attribution of Risk Categories:

Definite: Adverse event(s) will clearly be related to investigational agent(s) or other intervention

Probable: Adverse event(s) will likely be related to investigational agent(s)

Possible: Adverse event(s) may be related to investigational agent(s)

Unlikely: Adverse event(s) will doubtfully be related to investigational agent(s)

Unrelated: Adverse event(s) will clearly not be related to the investigational agents(s)

Grades of Risk:

0: No adverse event or within normal limits

1: Mild adverse event

2: Moderate adverse event

3: Severe adverse event resulting in hospitalization or prolongation of existing hospitalization, a persistent or significant disability/incapacity, or a congenital anomaly/birth defect

4: Life-threatening or disabling adverse event

5: Fatal adverse event

This process is described in more detail in the Data and Safety Monitoring Plan (attached).

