In the unlikely event that such events occur, serious and unanticipated and related adverse events or unanticipated problems involving risks to subjects or others will be reported immediately (if possible), followed by a written report within 7 calendar days of the Principal Investigator becoming aware of the

event to the Yale IRB, Independent Monitoring Monitor(s), and NCCIH. Any other unanticipated problem will be reported to the IRB, Independent Safety Monitor(s), and NCCIH within 14 days of the PI becoming aware of the problem.

To ensure that the design, conduct, and reporting of research for this project is free from bias resulting from Investigator financial conflicts of interest, the project will be conducted in accordance with NIH Financial Conflict of Interest (FCOI) regulation, *Responsibility of Applicants for Promoting Objectivity in Research for which PHS Funding is Sought* (42 CFR Part 50 Subpart F), applicable to grants and cooperative agreements (2011 Revised Regulations) and Yale University Policy on Conflict of Interest.

13. Statistical Considerations: Describe the statistical analyses that support the study design.

Overview: Quit is defined based on proposed standards [73] as 7 day point prevalence abstinence and continuous abstinence (<5 cigs since quit date). E-cigarette use will not constitute a relapse but will be monitored and reported. Ratings (Likert items, e.g., timeliness) will be evaluated as % of participants and score range (very low, low, moderate, high, very high), with feasibility determined by 75% of participants rating an item as moderate or higher. Average responses for a given factor (e.g., satisfaction) on the User Experiences Questionnaire will be tested similarly, and qualitative analysis of open-ended questions will be used to further evaluate acceptability. Adherence cut-offs (e.g., time spent wearing the smartband) will be 80%. Adherence was high in pilot work (90% of participants answered 80% of smoking notifications [14]).

Aim 1. To assess treatment fidelity for a smartband/smartphone-based mindfulness

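### The only Severe grade on the adverse-event scale is defined by seriousness outcomes, so some severe events have no proper grade and persistent or significant disability fits two

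*Combined protocol and SAP*

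**What the plan says.** Section 12 makes the principal investigator review all adverse events and "determine the attribution and grade of severity of the adverse event by using the following scales". The severity scale has six levels. Grade 0 is no event, Grade 1 is mild and Grade 2 is moderate, with neither of the last two defined further. Grade 3 is "Severe adverse event resulting in hospitalization or prolongation of existing hospitalization, a persistent or significant disability/incapacity, or a congenital anomaly/birth defect". Grade 4 is "Life-threatening or disabling adverse event". Grade 5 is fatal. No rule is given for an event that meets two levels.

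The grades feed the safety oversight described in the same section, where the principal investigator is responsible for "conducting quarterly safety reviews which will be provided for review to the Independent Study Monitoring Committee". In that review the investigator judges whether the study goes on unchanged, is modified, or closes to enrollment.

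Expedited reporting is set out separately. The first clause covers events by seriousness, expectedness and relatedness: "serious and unanticipated and related adverse events or unanticipated problems involving risks to subjects or others will be reported immediately (if possible"; a written report follows within 7 calendar days. The second reads "Any other unanticipated problem will be reported to the IRB, Independent Safety Monitor(s), and NCCIH within 14 days". The supplied text does not define serious.

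Section 12 presents this as a brief account of a formal monitoring plan that is attached to the protocol. That plan is not among the documents.

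**The concern.** Severity and seriousness are different properties of an adverse event. Severity describes how intense it is; seriousness describes what it led to. Section 12 asks for a grade of severity, but its Severe level can be reached only through hospitalization, disability or incapacity, or a birth defect. Intensity alone is never enough.

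The kind of event at issue is easy to picture. Under D.1 every participant sets a quit date at 30 days, and Section 10 lists nicotine withdrawal as a risk. In that list the word mild is attached to anxiety, while restlessness, irritability and poor concentration carry no intensity. Section 11 says withdrawal is uncomfortable but does not threaten life. A participant with intense withdrawal who is neither hospitalized nor disabled would have a severe event that the scale cannot record as Severe.

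What is at stake is the consistency of the safety tables that go to the monitoring committee. Two people applying the scale to the same event could record different grades, and a severe event could be tabulated as moderate.

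**Working it through.** No sample size, error rate or event count is involved, and the plan gives no figure to reproduce. The check sets test events against the literal wording of each grade in Section 12.

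- **Event A:** severe in intensity; no hospitalization, disability or birth defect; not life-threatening or fatal.
- **Event B:** severe, causing persistent or significant disability; not life-threatening or fatal.
- **Event C:** disabling, but the disability is neither persistent nor significant; no hospitalization; not life-threatening or fatal.

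| Grade | Requirement in short | A | B | C |
|---|---|---|---|---|
| 0 | no event | no | no | no |
| 1 | mild | no | no | no |
| 2 | moderate | no | no | no |
| 3 | severe, with a listed outcome | no | yes | no |
| 4 | life-threatening or disabling | no | yes | yes |
| 5 | fatal | no | no | no |
| Matches | | 0 of 6 | 2 of 6 | 1 of 6 |

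The result for A depends on reading Grades 1 and 2 as intensity levels. If the whole scale is instead read as graded by outcome, A falls to Grade 2 or below, because it has none of the outcomes named from Grade 3 upward. It is then a severe event recorded as Moderate at most. Neither reading gives the right answer.

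The overlap for B does not extend to every disabling event: C fits Grade 4 only.

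Next, where the grade is used. Section 12 has two reporting deadlines, 7 calendar days and 14 days. Neither mentions a grade, so 0 of 2 depend on it. The continue, modify or close decision carries no threshold expressed in grades. The feasibility criteria in Section 13 (75% of participants for ratings, 80% for adherence) do not involve adverse events. The grade therefore affects only how events are classified for the quarterly review.

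With Grade 3 defined by intensity and disability kept in Grade 4 only, A matches 1 of 6 (Grade 3), B matches 1 of 6 (Grade 4), and C is unchanged.

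**The case against.** The strongest reply is that Section 12 is a summary. A definition of each severity level and a rule for ties would normally sit in the attached plan. This stands as a limit on how firmly the point can be put. It does not remove it, because Section 12 states these as the scales the investigator uses and nothing in the supplied text corrects them.

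A second reply is that, on an ordered scale, one naturally assigns the highest level met, so Event B is simply Grade 4. That is reasonable, but it is not stated, and it would leave the disability wording in Grade 3 with little or nothing to do. No rule in the documents treats Grades 3 and 4 differently, so the overlap costs little either way.

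A third is that the study is low risk: "This project presents minimal risks to the subjects and adverse events or other problems are not anticipated". Section 12 rates it as minimal risk, and most withdrawal would fit Grades 1 and 2. This also stands, and it is why the point is minor.

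Two stronger readings are tempting. The first is that the attribution scale leaves the intervention uncovered, because four of its five categories name only investigational agents. The Definite category, however, reads "Adverse event(s) will clearly be related to investigational agent(s) or other intervention", the other four can be read as shorthand for it, Section II marks drugs, biologics and devices as not applicable, and only one intervention is under test. That is an editorial matter. The second is that this wording could delay a safety report. The documents do not support that: the reporting clauses do not refer to the attribution scale, and the faster clause separately covers unanticipated problems involving risk, whatever attribution is recorded.

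**Conclusion.** The point holds as a minor defect in the safety classification. A severe event without the listed outcomes that is not life-threatening, disabling or fatal either matches none of the six grades or is under-graded as Moderate. An event with persistent or significant disability matches two. The effect stops at the classification of events in the quarterly reviews.

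This rests on the wording of Section 12 as supplied and on the assumption that the attached plan does not already settle the definitions. The documents give no adverse-event rate, so the number of events affected cannot be estimated; given the risk level, it may be none.

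**What to change.** In Section 12, and in the attached plan if it carries the same scale:

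1. Define Grade 3 as severe in intensity and not meeting Grade 4 or 5, without requiring hospitalization, disability or birth defect.
2. Keep disability in one grade only. Grade 4 already names it.
3. Record seriousness as a separate yes/no item for each event, using the outcomes now listed under Grade 3 plus life-threatening and fatal. This also gives the expedited-reporting clause the definition of serious that the supplied text lacks.

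As an optional tidy-up, refer to the study intervention or procedures in all five attribution categories.

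The cost is a small wording amendment and one extra item on the adverse-event record. No new visits, staff or data collection from participants are needed. Some events may be graded 3 that would otherwise have been graded 2.

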Adherence to wearing the smartband will be monitored daily and participants will be sent automated reminders and/or text message reminders if their smartband is not active for 12-24 hours, followed by a phone call if their smartband is not active for 2 days. As an incentive, participants will be paid \$1/day to wear the smartband during waking hours (≥ 12 hours/day; current smartband battery life is 3 days). Mindfulness and RAIN exercise completions will also be monitored daily, and participants will be sent either a rewarding text message if there is at least one completion from the day before, or an encouraging text message if the participant did not complete any exercises the day before. Additionally, to encourage participation in mindfulness training, we will add \$10 for completing the initial mindfulness instructions. Finally, there will be a study completion bonus of \$50.

To improve adherence, study compensation will be: \$10 upon completion of the zoom/online training, \$20 upon completion of the second study survey, and \$10 upon completion of the third study survey. At the end of the study, they will be paid \$1 per day for each day of the 60-day study that they have worn their smartband for 12 waking hours (up to \$60). At the end of the study, they will also be paid \$10 for the end of study survey, and a \$50 bonus payment if they have completed all parts of the study. **Total study payment will be up to \$160** (up to \$40 paid upon each survey completion, up to \$120 paid at

the end of the study). Please note that all study equipment (smartband, CO-monitor, if applicable) must be returned before the final study payment. Finally, they may be invited to take part in an optional debriefing at the end of the study, for which they will be paid an additional \$10.

5. Genetic Testing N/A

6. **Subject Population:** Provide a detailed description of the types of human subjects who will be recruited into this study.

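### RAIN delivery is scored only at prompts that were sent and answered, so a smoking profile that under-predicts can still pass Aim 1(3)

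*Combined protocol and SAP*

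**What the plan says.** For RAIN, Section 13, Aim 1(3) reads: "Whether we can deliver RAIN to predicted smoking episodes will be measured as average timeliness ratings in the next 30 days of the study". It adds "craving ratings obtained before participants complete RAIN" as a proxy for having targeted moments of high craving. The pass rule is "feasibility determined by 75% of participants rating an item (timeliness, craving) as moderate or higher". D.8c fixes when the timeliness item appears: "After completing RAIN, they will be asked". The first craving rating opens the same prompt.

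The other two fidelity measures are built differently. Aim 1(1) uses "the percent of smoking episodes detected and the rate of false alarms in the first 21 days of the study", and Aim 1(2) uses correct triggers and false alarms over the following 7 days. Neither extends into the RAIN phase.

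On prediction, D.9 says: "Individualized smoking profiles will be obtained using smartband data tracking smoking across the first 21 days of the study". The profile draws on average smoking times, time between cigarettes, wake and sleep times and cigarettes per day. For less predictable smokers, waking time is split into as many intervals as cigarettes per day, with one randomly timed prompt in each. D.9 also names the amount of tracking data needed for an adequate profile as a main question of the trial.

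Smoking is still recorded after the quit date: under D.1, "any detected smoking episode (i.e., relapse) will trigger the mindful smoking exercise". D.7 lets users report undetected cigarettes.

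**The concern.** A rating attached to a prompt describes that prompt. It says nothing about smoking times for which no prompt was scheduled. A profile that finds a few regular moments and misses the rest can earn good timeliness and craving ratings and be called feasible. The trial is meant to inform a larger efficacy trial, so the question of whether 21 days of tracking predicts smoking well enough would go forward without a measure that answers it. The data for such a measure are already being collected.

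**Working it through.** The plan derives no sample size, power or error rate for the RAIN criterion, so there is no figure of its own to reproduce. The check asks what can enter the score, then illustrates size.

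**1. What each measure can see**

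| Measure | Period | Unit scored | Sees an episode with no prompt? |
|---|---|---|---|
| Aim 1(1) detection | days 1-21 | smoking episodes | yes, if self-reported |
| Aim 1(2) mindful smoking triggers | next 7 days | triggers from detected smoking | not about RAIN |
| Aim 1(3) timeliness | 30 days post-quit | completed RAIN exercises | no |
| Aim 1(3) craving | 30 days post-quit | answered RAIN prompts | no |
| Aim 2(5) RAIN completion | 30 days post-quit | RAIN exercises | no |

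**2. The pass rule.** With n = 100 and p the chance that a participant's rating is moderate or higher (assumed), the chance of passing is P(X ≥ 75), X ~ Binomial(100, p). This gives 16.3% at p = 0.70, 55.4% at 0.75, 91.3% at 0.80 and 99.7% at 0.85. With 53 raters (the earlier app trial's 53% completers applied to 100, rule 40 or more) it is 23.9%, 54.2%, 84.1% and 97.8%. The share of smoking times that received a prompt is not in the formula. With p held at 0.85, a simulation of 2,000 trials passes the rule in 99.7-99.8% whether that share is 100%, 75%, 50% or 25%. This follows from the construction: coverage and ratings were taken as independent.

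**3. What could go unscored.** Take 12 habitual smoking times a day, the mean in the earlier smartband study quoted under Aim 2. Over 30 days that is 12 × 30 = 360.
- Profile predicts 9 a day: 270 prompts, 90 times without RAIN (coverage 75%).
- Predicts 6: 180 prompts, 180 without (50%).
- Predicts 3: 90 prompts, 270 without (25%).

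At 50% coverage with 80% of prompts answered (assumed), 180 × 0.80 = 144 rated prompts stand for 360 smoking times. Smoking should fall after the quit date, so 12 a day is an upper-end illustration of habitual times, not a forecast of lapses.

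**4. How far a profile might fall short.** Captured share = wear × (detected share + self-reported share of misses). The plan's 80% adherence cut-off serves as wear, and the lower edge of its expected detection (above 80%) as the detected share. Smoking is assumed even over waking hours, with nothing imputed for unworn time.
- No self-reported misses: 0.80 × 0.80 = 0.64, or 12 × 0.64 = 7.68 of 12 a day.
- All misses in worn time reported: 0.80 × (0.80 + 0.20) = 0.80, or 9.6 of 12.
- Full wear and full reporting: 1.00.

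**5. Why post-quit coverage cannot be the criterion.** Suppose RAIN precedes 9 of 12 habitual times (75%) and averts 6 of those 9 cigarettes. Then 3 preceded and 3 unpreceded cigarettes remain. Measured coverage is 3/6 = 50%, and 6/9 = 67% of prompts are followed by no cigarette, though those are the successes.

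**The case against.** Several existing elements bear on the problem. Wear is measured against 80%, and detection counts self-reported misses, so the two likeliest causes of a poor profile are visible. Craving is a second check with the same threshold. The User Experiences Questionnaire asks about timing and dose, and the acceptability of the number of interventions is evaluated. The D.9 fallback ties prompt count to cigarettes per day. The missing-data plan covers ratings, and the plan promises to report other aspects of fidelity. Some missed episodes may also draw ratings toward the too-late end. Finally, Aim 1(3) speaks of predicted episodes, not every episode.

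This softens the concern but does not answer it. None of these compares smoking times with prompts. A delivered but unrated prompt might be imputed; an episode with no prompt has no record to impute. The fallback prompts fall at random times, and D.9 lists cigarettes per day among the items taken from band data. Restricting the aim to predicted episodes leaves D.9's question about the profile without a measure.

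A reader might infer that cigarettes smoked with the band off are certainly absent from the profile and never adjusted for. The documents do not establish this. They are silent on unworn time, say the profile uses as much information as possible, and do not exclude self-reported misses. A reader might also want a post-quit coverage threshold. That would condition on lapsing, penalise RAIN when it works, and still miss band-off cigarettes that nobody reports.

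**Conclusion.** The gap is real. Aim 1(3) has no term for smoking times that the profile failed to predict, so meeting the 75% rule shows that the prompts sent and answered were rated as timely, not that the profile was adequate. How large the shortfall would be cannot be derived from the documents. The 64% and 80% figures rest on threshold wear and detection, even smoking over waking hours and no filling of unworn time; they show what is possible and are not estimates. The insensitivity of the pass rule assumes that ratings do not depend on coverage. Any link through too-late ratings would weaken the problem without removing it. This is a worthwhile, inexpensive improvement to a feasibility trial, not a flaw that invalidates its other aims.

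**What to change.** Add a prediction-accuracy measure to Aim 1(3), leaving the prompting unchanged.

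(a) Apply the day 1-21 profile to the pre-quit days after day 21, when no RAIN is sent. Per participant, report the percent of detected or self-reported cigarettes that fall within a prespecified window after a predicted prompt time, and the percent of predicted prompt times with no cigarette in that window.

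(b) Report RAIN prompts delivered per day against days 1-21 cigarettes per day computed on worn time, and against the day-21 Time Line Follow Back count in Table 1. The latter does not depend on the band, so it can show band-off smoking.

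(c) Report post-quit coverage among participants who lapse, and prompts followed by no cigarette, as description only.

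Interpret the timeliness result together with (a) and (b).

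The cost is SAP wording and modest analysis of data already planned, provided the predicted prompt times can be exported for the pre-quit days. There are three limits. Pre-quit smoking may already be changing under the mindful smoking exercise. The time stamp of a self-report may lag the cigarette. The fidelity result may look less favourable.
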